**Programming Note:**

- Include all SOC and all PTERMs.

Sponsor: Lumen Bioscience, Inc.  
 Protocol: CAM01

Database Lock: yyyy-mm-dd

Table 14.3.3.5 Summary of Treatment-Emergent Adverse Events by Relationship, by SOC and PT (Safety Analysis Set)

System Organ Class (SOC) Preferred Term (PT) Causality	Part A:		Part B:		LMN-101 Overall (N=xxx) n (%) m	Placebo (N=xxx) n (%) m	Overall (N=xxx) n (%) m
	LMN-101 3000 mg (N=xxx)	LMN-101 300 mg (N=xxx)	LMN-101 1000 mg (N=xxx)	LMN-101 3000 mg (N=xxx)			
	n (%) m	n (%) m	n (%) m	n (%) m			
Subjects with at least one TEAE	xx (xx.x%) xx	xx (xx.x%) xx	xx (xx.x%) xx	xx (xx.x%) xx	xx (xx.x%) xx	xx (xx.x%) xx	xx (xx.x%) xx
Mild	xx (xx.x%) xx	xx (xx.x%) xx	xx (xx.x%) xx	xx (xx.x%) xx	xx (xx.x%) xx	xx (xx.x%) xx	xx (xx.x%) xx
Moderate	xx (xx.x%) xx	xx (xx.x%) xx	xx (xx.x%) xx	xx (xx.x%) xx	xx (xx.x%) xx	xx (xx.x%) xx	xx (xx.x%) xx
Severe	xx (xx.x%) xx	xx (xx.x%) xx	xx (xx.x%) xx	xx (xx.x%) xx	xx (xx.x%) xx	xx (xx.x%) xx	xx (xx.x%) xx
Life-threatening	xx (xx.x%) xx	xx (xx.x%) xx	xx (xx.x%) xx	xx (xx.x%) xx	xx (xx.x%) xx	xx (xx.x%) xx	xx (xx.x%) xx
Death	xx (xx.x%) xx	xx (xx.x%) xx	xx (xx.x%) xx	xx (xx.x%) xx	xx (xx.x%) xx	xx (xx.x%) xx	xx (xx.x%) xx
SOC1	xx (xx.x%) xx	xx (xx.x%) xx	xx (xx.x%) xx	xx (xx.x%) xx	xx (xx.x%) xx	xx (xx.x%) xx	xx (xx.x%) xx
PT1	xx (xx.x%) xx	xx (xx.x%) xx	xx (xx.x%) xx	xx (xx.x%) xx	xx (xx.x%) xx	xx (xx.x%) xx	xx (xx.x%) xx
Unrelated	xx (xx.x%) xx	xx (xx.x%) xx	xx (xx.x%) xx	xx (xx.x%) xx	xx (xx.x%) xx	xx (xx.x%) xx	xx (xx.x%) xx
Possibly Related	xx (xx.x%) xx	xx (xx.x%) xx	xx (xx.x%) xx	xx (xx.x%) xx	xx (xx.x%) xx	xx (xx.x%) xx	xx (xx.x%) xx
Probably Related	xx (xx.x%) xx	xx (xx.x%) xx	xx (xx.x%) xx	xx (xx.x%) xx	xx (xx.x%) xx	xx (xx.x%) xx	xx (xx.x%) xx
SOC2	xx (xx.x%) xx	xx (xx.x%) xx	xx (xx.x%) xx	xx (xx.x%) xx	xx (xx.x%) xx	xx (xx.x%) xx	xx (xx.x%) xx
PT1	xx (xx.x%) xx	xx (xx.x%) xx	xx (xx.x%) xx	xx (xx.x%) xx	xx (xx.x%) xx	xx (xx.x%) xx	xx (xx.x%) xx
Unrelated	xx (xx.x%) xx	xx (xx.x%) xx	xx (xx.x%) xx	xx (xx.x%) xx	xx (xx.x%) xx	xx (xx.x%) xx	xx (xx.x%) xx
Possibly Related	xx (xx.x%) xx	xx (xx.x%) xx	xx (xx.x%) xx	xx (xx.x%) xx	xx (xx.x%) xx	xx (xx.x%) xx	xx (xx.x%) xx
Probably Related	xx (xx.x%) xx	xx (xx.x%) xx	xx (xx.x%) xx	xx (xx.x%) xx	xx (xx.x%) xx	xx (xx.x%) xx	xx (xx.x%) xx
Etc.							

Note: A treatment-emergent adverse event (TEAE) is defined as an adverse event that occurred or worsened following the first administration of study drug. If a subject has multiple occurrences of a TEAE, the subject is presented only once in the Subject count (n) column for a given System Organ Class and Preferred Term. Occurrences are counted each time in the mentions/Occurrence (m) column.

MedDRA Version xx.x

**Programming Note:**

- Include all SOCs and all PTERMs.

Sponsor: Lumen Bioscience, Inc.  
Protocol: CAM01

Database Lock: yyyy-mm-dd

Table 14.3.4.1.1 Summary of Hematology & Coagulation by Timepoint (Safety Analysis Set)

Parameter: Hemoglobin (g/L)

Treatment Group Visit	Actual Value						Change from Baseline 					
	n	Mean	SD	Median	Minimum	Maximum	n	Mean	SD	Median	Minimum	Maximum
Part A: LMN-101 3000 mg (N=xx)												
Baseline 	xx	xx.xx	xx.xx	xx.xx	xx.x	xx.x	-	-	-	-	-	-
Day 8	xx	xx.xx	xx.xx	xx.xx	xx.x	xx.x	xx	xx.xx	xx.xx	xx.xx	xx.x	xx.x
Day 15	xx	xx.xx	xx.xx	xx.xx	xx.x	xx.x	xx	xx.xx	xx.xx	xx.xx	xx.x	xx.x
Day 29	xx	xx.xx	xx.xx	xx.xx	xx.x	xx.x	xx	xx.xx	xx.xx	xx.xx	xx.x	xx.x
Part B: LMN-101 300 mg (N=xx)												
Baseline 	xx	xx.xx	xx.xx	xx.xx	xx.x	xx.x	-	-	-	-	-	-
Day 8	xx	xx.xx	xx.xx	xx.xx	xx.x	xx.x	xx	xx.xx	xx.xx	xx.xx	xx.x	xx.x
Day 15	xx	xx.xx	xx.xx	xx.xx	xx.x	xx.x	xx	xx.xx	xx.xx	xx.xx	xx.x	xx.x
Day 28	xx	xx.xx	xx.xx	xx.xx	xx.x	xx.x	xx	xx.xx	xx.xx	xx.xx	xx.x	xx.x
Day 56	xx	xx.xx	xx.xx	xx.xx	xx.x	xx.x	xx	xx.xx	xx.xx	xx.xx	xx.x	xx.x

etc.

SD: Standard Deviation

Baseline is defined as the last valid, non-missing assessment prior to study drug administration on Day 1.**Programming Note:**

- Include all treatment groups: Part A: LMN-101 3000 mg, Part B: LMN-101 300 mg, Part B: LMN-101 1000 mg, Part B: LMN-101 3000 mg, LMN-101 Overall, Placebo and Overall.
- Include all scheduled visits/time points and all Hematology and Coagulation parameters.
- Produce change from baseline and change from follow up tables.

Program: filepath\_name, Output Name: filepath\_name Creation Date/Time: DDMMYYYY HH:MM

Page 1 of xx

Sponsor: Lumen Bioscience, Inc.  
 Protocol: CAM01

Database Lock: yyyy-mm-dd

Table 14.3.4.1.1 Summary of Hematology & Coagulation by Timepoint (Safety Analysis Set) - Continued

Parameter: Hemoglobin (g/L)

Treatment Group Visit	Actual Value						Change from Follow-up 					
	n	Mean	SD	Median	Minimum	Maximum	n	Mean	SD	Median	Minimum	Maximum
Part A: LMN-101 3000 mg (N=xx)												
Screening	xx	xx.xx	xx.xx	xx.xx	xx.x	xx.x	xx	xx.xx	xx.xx	xx.xx	xx.x	xx.x
Day 1 Pre dose	xx	xx.xx	xx.xx	xx.xx	xx.x	xx.x	xx	xx.xx	xx.xx	xx.xx	xx.x	xx.x
Day 8	xx	xx.xx	xx.xx	xx.xx	xx.x	xx.x	xx	xx.xx	xx.xx	xx.xx	xx.x	xx.x
Day 15	xx	xx.xx	xx.xx	xx.xx	xx.x	xx.x	xx	xx.xx	xx.xx	xx.xx	xx.x	xx.x
Follow-up	xx	xx.xx	xx.xx	xx.xx	xx.x	xx.x	-	-	-	-	-	-
Part B: LMN-101 300 mg (N=xx)												
Screening	xx	xx.xx	xx.xx	xx.xx	xx.x	xx.x	xx	xx.xx	xx.xx	xx.xx	xx.x	xx.x
Day 1 Pre dose	xx	xx.xx	xx.xx	xx.xx	xx.x	xx.x	xx	xx.xx	xx.xx	xx.xx	xx.x	xx.x
Day 8	xx	xx.xx	xx.xx	xx.xx	xx.x	xx.x	xx	xx.xx	xx.xx	xx.xx	xx.x	xx.x
Day 15	xx	xx.xx	xx.xx	xx.xx	xx.x	xx.x	xx	xx.xx	xx.xx	xx.xx	xx.x	xx.x
Day 28	xx	xx.xx	xx.xx	xx.xx	xx.x	xx.x	xx	xx.xx	xx.xx	xx.xx	xx.x	xx.x
Follow-up	xx	xx.xx	xx.xx	xx.xx	xx.x	xx.x	-	-	-	-	-	-

etc.

SD: Standard Deviation

 Follow up result is defined as the Day 29 result for Part A and Day 56 result for Part B.

Sponsor: Lumen Bioscience, Inc.  
Protocol: CAM01

Database Lock: yyyy-mm-dd

Table 14.3.4.1.2 Summary of Hematology & Coagulation Shifts from Baseline (Low, Normal, High) (Safety Analysis Set)

Parameter: Hemoglobin (g/L)

Treatment Visit	Baseline Result Classification	Post-dose Result Classification			
		Baseline  n(%)	Low	Normal	High
Part A: LMN-101 3000 mg (N=xx)					
Day 8					
n		xx	xx	xx	xx
Low		xx (xx.x%)	xx (xx.x%)	xx (xx.x%)	xx (xx.x%)
Normal		xx (xx.x%)	xx (xx.x%)	xx (xx.x%)	xx (xx.x%)
High		xx (xx.x%)	xx (xx.x%)	xx (xx.x%)	xx (xx.x%)
Day 15					
n		xx	xx	xx	xx
Low		xx (xx.x%)	xx (xx.x%)	xx (xx.x%)	xx (xx.x%)
Normal		xx (xx.x%)	xx (xx.x%)	xx (xx.x%)	xx (xx.x%)
High		xx (xx.x%)	xx (xx.x%)	xx (xx.x%)	xx (xx.x%)
Day 29					
n		xx	xx	xx	xx
Low		xx (xx.x%)	xx (xx.x%)	xx (xx.x%)	xx (xx.x%)
Normal		xx (xx.x%)	xx (xx.x%)	xx (xx.x%)	xx (xx.x%)
High		xx (xx.x%)	xx (xx.x%)	xx (xx.x%)	xx (xx.x%)
etc.					

Baseline is defined as the last valid, non-missing assessment prior to study drug administration on Day 1. Percentages are based on the number of subjects with data at the specific visit.

## Programming Note:

- Include all treatment groups: Part A: LMN-101 3000 mg, Part B: LMN-101 300 mg, Part B: LMN-101

Sponsor: Lumen Bioscience, Inc.  
 Protocol: CAM01

Database Lock: yyyy-mm-dd

Table 14.3.4.1.3 Summary of Hematology & Coagulation Shifts from Follow-up (Low, Normal, High) (Safety Analysis Set)

Parameter: Hemoglobin (g/L)

Treatment Visit	Follow-up  n(%)	Result Classification		
		Low	Normal	High
Part A: LMN-101 3000 mg (N=xx)				
Screening				
n	xx	xx	xx	xx
Low	xx (xx.x%)	xx (xx.x%)	xx (xx.x%)	xx (xx.x%)
Normal	xx (xx.x%)	xx (xx.x%)	xx (xx.x%)	xx (xx.x%)
High	xx (xx.x%)	xx (xx.x%)	xx (xx.x%)	xx (xx.x%)
Day 1 Pre dose				
n	xx	xx	xx	xx
Low	xx (xx.x%)	xx (xx.x%)	xx (xx.x%)	xx (xx.x%)
Normal	xx (xx.x%)	xx (xx.x%)	xx (xx.x%)	xx (xx.x%)
High	xx (xx.x%)	xx (xx.x%)	xx (xx.x%)	xx (xx.x%)
Day 8				
n	xx	xx	xx	xx
Low	xx (xx.x%)	xx (xx.x%)	xx (xx.x%)	xx (xx.x%)
Normal	xx (xx.x%)	xx (xx.x%)	xx (xx.x%)	xx (xx.x%)
High	xx (xx.x%)	xx (xx.x%)	xx (xx.x%)	xx (xx.x%)
etc.				

 Follow up result is defined as the Day 29 result for Part A and Day 56 result for Part B. Percentages are based on the number of subjects with data at the specific visit.

**Programming Note:**

- Include all treatment groups: Part A: LMN-101 3000 mg, Part B: LMN-101 300 mg, Part B: LMN-101

Sponsor: Lumen Bioscience, Inc.  
Protocol: CAM01

Database Lock: yyyy-mm-dd

Table 14.3.4.2.1 Summary of Serum Chemistry by Timepoint (Safety Analysis Set)

Parameter: Sodium (g/L)

Treatment Group Visit	Actual Value						Change from Baseline 					
	n	Mean	SD	Median	Minimum	Maximum	n	Mean	SD	Median	Minimum	Maximum
Part A: LMN-101 3000 mg (N=xx)												
Baseline 	xx	xx.xx	xx.xx	xx.xx	xx.x	xx.x	-	-	-	-	-	-
Day 8	xx	xx.xx	xx.xx	xx.xx	xx.x	xx.x	xx	xx.xx	xx.xx	xx.xx	xx.x	xx.x
Day 15	xx	xx.xx	xx.xx	xx.xx	xx.x	xx.x	xx	xx.xx	xx.xx	xx.xx	xx.x	xx.x
Day 29	xx	xx.xx	xx.xx	xx.xx	xx.x	xx.x	xx	xx.xx	xx.xx	xx.xx	xx.x	xx.x
Part B: LMN-101 300 mg (N=xx)												
Baseline 	xx	xx.xx	xx.xx	xx.xx	xx.x	xx.x	-	-	-	-	-	-
Day 8	xx	xx.xx	xx.xx	xx.xx	xx.x	xx.x	xx	xx.xx	xx.xx	xx.xx	xx.x	xx.x
Day 15	xx	xx.xx	xx.xx	xx.xx	xx.x	xx.x	xx	xx.xx	xx.xx	xx.xx	xx.x	xx.x
Day 28	xx	xx.xx	xx.xx	xx.xx	xx.x	xx.x	xx	xx.xx	xx.xx	xx.xx	xx.x	xx.x
Day 56	xx	xx.xx	xx.xx	xx.xx	xx.x	xx.x	xx	xx.xx	xx.xx	xx.xx	xx.x	xx.x

etc.

SD: Standard Deviation

Baseline is defined as the last valid, non-missing assessment prior to study drug administration on Day 1.

**Programming Note:**

- Include all treatment groups: AR882 25mg, AR882 50mg, AR882 75mg, AR882 Overall, Placebo.
- Include all scheduled visits/time points and all Serum Chemistry parameters.
- Serum Creatinine (safety) is also evaluated on: Day 4 and Day 6.

Sponsor: Lumen Bioscience, Inc.  
 Protocol: CAM01

Database Lock: yyyy-mm-dd

Table 14.3.4.2.1 Summary of Serum Chemistry by Timepoint (Safety Analysis Set) - Continued

Parameter: Sodium (g/L)

Treatment Group Visit	Actual Value						Change from Follow up 					
	n	Mean	SD	Median	Minimum	Maximum	n	Mean	SD	Median	Minimum	Maximum
Part A: LMN-101 3000 mg (N=xx)												
Screening	xx	xx.xx	xx.xx	xx.xx	xx.x	xx.x	xx	xx.xx	xx.xx	xx.xx	xx.x	xx.x
Day 1 Pre dose	xx	xx.xx	xx.xx	xx.xx	xx.x	xx.x	xx	xx.xx	xx.xx	xx.xx	xx.x	xx.x
Day 8	xx	xx.xx	xx.xx	xx.xx	xx.x	xx.x	xx	xx.xx	xx.xx	xx.xx	xx.x	xx.x
Day 15	xx	xx.xx	xx.xx	xx.xx	xx.x	xx.x	xx	xx.xx	xx.xx	xx.xx	xx.x	xx.x
Follow-up	xx	xx.xx	xx.xx	xx.xx	xx.x	xx.x	-	-	-	-	-	-
Part B: LMN-101 300 mg (N=xx)												
Screening	xx	xx.xx	xx.xx	xx.xx	xx.x	xx.x	xx	xx.xx	xx.xx	xx.xx	xx.x	xx.x
Day 1 Pre dose	xx	xx.xx	xx.xx	xx.xx	xx.x	xx.x	xx	xx.xx	xx.xx	xx.xx	xx.x	xx.x
Day 8	xx	xx.xx	xx.xx	xx.xx	xx.x	xx.x	xx	xx.xx	xx.xx	xx.xx	xx.x	xx.x
Day 15	xx	xx.xx	xx.xx	xx.xx	xx.x	xx.x	xx	xx.xx	xx.xx	xx.xx	xx.x	xx.x
Day 28	xx	xx.xx	xx.xx	xx.xx	xx.x	xx.x	xx	xx.xx	xx.xx	xx.xx	xx.x	xx.x
Follow-up	xx	xx.xx	xx.xx	xx.xx	xx.x	xx.x	-	-	-	-	-	-
etc.												

SD: Standard Deviation

 Follow up result is defined as the Day 29 result for Part A and Day 56 result for Part B.

Sponsor: Lumen Bioscience, Inc.  
Protocol: CAM01

Database Lock: yyyy-mm-dd

Table 14.3.4.2.2 Summary of Serum Chemistry Shifts from Baseline (Low, Normal, High) (Safety Analysis Set)

Parameter: Sodium (g/L)

Treatment Visit	Baseline Result Classification	Baseline  n(%)	Post-dose Result Classification		
			Low	Normal	High
LMN-101 25 mg (N=xx)					
Day 2					
n		xx	xx	xx	xx
Low		xx	xx (xx.x%)	xx (xx.x%)	xx (xx.x%)
Normal		xx	xx (xx.x%)	xx (xx.x%)	xx (xx.x%)
High		xx	xx (xx.x%)	xx (xx.x%)	xx (xx.x%)
Day 5					
N		xx	xx	xx	xx
Low		xx	xx (xx.x%)	xx (xx.x%)	xx (xx.x%)
Normal		xx	xx (xx.x%)	xx (xx.x%)	xx (xx.x%)
High		xx	xx (xx.x%)	xx (xx.x%)	xx (xx.x%)
Day 6					
n		xx	xx	xx	xx
Low		xx	xx (xx.x%)	xx (xx.x%)	xx (xx.x%)
Normal		xx	xx (xx.x%)	xx (xx.x%)	xx (xx.x%)
High		xx	xx (xx.x%)	xx (xx.x%)	xx (xx.x%)
etc.					

Baseline is defined as the last valid, non-missing assessment prior to study drug administration on Day 1. Percentages are based on the number of subjects with data at the specific visit.

**Programming Note:**

- Include all treatment groups: AR882 25mg, AR882 50mg, AR882 75mg, AR882 Overall, Placebo.
- Include all scheduled visits/time points and all Serum Chemistry parameters.
- Serum Creatinine (safety) is also evaluated on: Day 4 and Day 6.

Sponsor: Lumen Bioscience, Inc.  
Protocol: CAM01

Database Lock: yyyy-mm-dd

Table 14.3.4.2.3 Summary of Serum Chemistry Shifts from Follow up (Low, Normal, High) (Safety Analysis Set)

Parameter: Sodium (g/L)

Treatment Visit	Follow-up Result Classification	Follow-up  n (%)	Result Classification		
			Low	Normal	High
Part A: LMN-101 3000 mg (N=xx)					
Screening					
n		xx	xx	xx	xx
Low		xx (xx.x%)	xx (xx.x%)	xx (xx.x%)	xx (xx.x%)
Normal		xx (xx.x%)	xx (xx.x%)	xx (xx.x%)	xx (xx.x%)
High		xx (xx.x%)	xx (xx.x%)	xx (xx.x%)	xx (xx.x%)
Day 1 Pre dose					
n		xx	xx	xx	xx
Low		xx (xx.x%)	xx (xx.x%)	xx (xx.x%)	xx (xx.x%)
Normal		xx (xx.x%)	xx (xx.x%)	xx (xx.x%)	xx (xx.x%)
High		xx (xx.x%)	xx (xx.x%)	xx (xx.x%)	xx (xx.x%)
Day 8					
n		xx	xx	xx	xx
Low		xx (xx.x%)	xx (xx.x%)	xx (xx.x%)	xx (xx.x%)
Normal		xx (xx.x%)	xx (xx.x%)	xx (xx.x%)	xx (xx.x%)
High		xx (xx.x%)	xx (xx.x%)	xx (xx.x%)	xx (xx.x%)
etc.					

 Follow up result is defined as the Day 29 result for Part A and Day 56 result for Part B.  
Percentages are based on the number of subjects with data at the specific visit.

Sponsor: Lumen Bioscience, Inc.  
 Protocol: CAM01

Database Lock: yyyy-mm-dd

Table 14.3.4.4.1 Summary of Vital Signs by Timepoint (Safety Analysis Set)

Parameter: Systolic Blood Pressure (mmHg)

Treatment Group Visit	Actual Value						Change from Baseline 					
	n	Mean	SD	Median	Minimum	Maximum	n	Mean	SD	Median	Minimum	Maximum
Part A: LMN-101 3000 mg (N=xx)												
Baseline 	xx	xx.xx	xx.xx	xx.xx	xx.x	xx.x	-	-	-	-	-	-
Day 1: 2 Hour Post-dose	xx	xx.xx	xx.xx	xx.xx	xx.x	xx.x	xx	xx.xx	xx.xx	xx.xx	xx.x	xx.x
Day 2	xx	xx.xx	xx.xx	xx.xx	xx.x	xx.x	xx	xx.xx	xx.xx	xx.xx	xx.x	xx.x
Day 8	xx	xx.xx	xx.xx	xx.xx	xx.x	xx.x	xx	xx.xx	xx.xx	xx.xx	xx.x	xx.x
Day 15	xx	xx.xx	xx.xx	xx.xx	xx.x	xx.x	xx	xx.xx	xx.xx	xx.xx	xx.x	xx.x
Day 29	xx	xx.xx	xx.xx	xx.xx	xx.x	xx.x	xx	xx.xx	xx.xx	xx.xx	xx.x	xx.x
Part B LMN-101 300 mg (N=xx)												
Baseline 	xx	xx.xx	xx.xx	xx.xx	xx.x	xx.x	-	-	-	-	-	-
Day 1: 2 Hour Post-dose	xx	xx.xx	xx.xx	xx.xx	xx.x	xx.x	xx	xx.xx	xx.xx	xx.xx	xx.x	xx.x
Day 2	xx	xx.xx	xx.xx	xx.xx	xx.x	xx.x	xx	xx.xx	xx.xx	xx.xx	xx.x	xx.x
Day 8	xx	xx.xx	xx.xx	xx.xx	xx.x	xx.x	xx	xx.xx	xx.xx	xx.xx	xx.x	xx.x
Day 15	xx	xx.xx	xx.xx	xx.xx	xx.x	xx.x	xx	xx.xx	xx.xx	xx.xx	xx.x	xx.x
Day 28	xx	xx.xx	xx.xx	xx.xx	xx.x	xx.x	xx	xx.xx	xx.xx	xx.xx	xx.x	xx.x
Day 56	xx	xx.xx	xx.xx	xx.xx	xx.x	xx.x	xx	xx.xx	xx.xx	xx.xx	xx.x	xx.x
etc.												

SD: Standard Deviation

Baseline is defined as the last valid, non-missing assessment prior to study drug administration on Day 1.

**Programming Note:**

- Include all treatment groups: Part A: LMN-101 3000 mg, Part B: LMN-101 300 mg, Part B: LMN-101 1000 mg, Part B: LMN-101 3000 mg, LMN-101 Overall, Placebo.
- Produce separate tables for change from baseline and change from follow-up

Sponsor: Lumen Bioscience, Inc.  
 Protocol: CAM01

Database Lock: yyyy-mm-dd

Table 14.3.4.4.1 Summary of Vital Signs by Timepoint (Safety Analysis Set) - Continued

Parameter: Systolic Blood Pressure (mmHg)

Treatment Group Visit	Actual Value						Change from Follow-up 					
	n	Mean	SD	Median	Minimum	Maximum	n	Mean	SD	Median	Minimum	Maximum
Part A: LMN-101 3000 mg (N=xx)												
Screening	xx	xx.xx	xx.xx	xx.xx	xx.x	xx.x	xx	xx.xx	xx.xx	xx.xx	xx.x	xx.x
Day 1: Pre-dose	xx	xx.xx	xx.xx	xx.xx	xx.x	xx.x	xx	xx.xx	xx.xx	xx.xx	xx.x	xx.x
Day 1: 2 Hour Post-dose	xx	xx.xx	xx.xx	xx.xx	xx.x	xx.x	xx	xx.xx	xx.xx	xx.xx	xx.x	xx.x
Day 2	xx	xx.xx	xx.xx	xx.xx	xx.x	xx.x	xx	xx.xx	xx.xx	xx.xx	xx.x	xx.x
Day 8	xx	xx.xx	xx.xx	xx.xx	xx.x	xx.x	xx	xx.xx	xx.xx	xx.xx	xx.x	xx.x
Day 15	xx	xx.xx	xx.xx	xx.xx	xx.x	xx.x	xx	xx.xx	xx.xx	xx.xx	xx.x	xx.x
Follow-up 	xx	xx.xx	xx.xx	xx.xx	xx.x	xx.x	-	-	-	-	-	-
Part B LMN-101 300 mg (N=xx)												
Screening	xx	xx.xx	xx.xx	xx.xx	xx.x	xx.x	xx	xx.xx	xx.xx	xx.xx	xx.x	xx.x
Day 1: Pre-dose	xx	xx.xx	xx.xx	xx.xx	xx.x	xx.x	xx	xx.xx	xx.xx	xx.xx	xx.x	xx.x
Day 1: 2 Hour Post-dose	xx	xx.xx	xx.xx	xx.xx	xx.x	xx.x	xx	xx.xx	xx.xx	xx.xx	xx.x	xx.x
Day 2	xx	xx.xx	xx.xx	xx.xx	xx.x	xx.x	xx	xx.xx	xx.xx	xx.xx	xx.x	xx.x
Day 8	xx	xx.xx	xx.xx	xx.xx	xx.x	xx.x	xx	xx.xx	xx.xx	xx.xx	xx.x	xx.x
Day 15	xx	xx.xx	xx.xx	xx.xx	xx.x	xx.x	xx	xx.xx	xx.xx	xx.xx	xx.x	xx.x
Day 28	xx	xx.xx	xx.xx	xx.xx	xx.x	xx.x	xx	xx.xx	xx.xx	xx.xx	xx.x	xx.x
Follow-up 	xx	xx.xx	xx.xx	xx.xx	xx.x	xx.x	-	-	-	-	-	-

etc.

SD: Standard Deviation

 Follow up result is defined as the Day 29 result for Part A and Day 56 result for Part B.

**Programming Note:**

- Include all treatment groups: Part A: LMN-101 3000 mg, Part B: LMN-101 300 mg, Part B: LMN-101 1000 mg, Part B: LMN-101 3000 mg, LMN-101 Overall, Placebo.
- Produce separate tables for change from baseline and change from follow-up

Sponsor: Lumen Bioscience, Inc. Database Lock: yyyy-mm-dd  
 Protocol: CAM01

Table 14.3.4.4.2 Summary of Vital Signs Shifts from Baseline (Low, Normal, High) (Safety Analysis Set)

Parameter: Systolic Blood Pressure (mmHg)

Treatment Visit	Baseline  n(%)	Post-dose Result Classification		
		Low	Normal	High
Part A: LMN-101 3000 mg(N=xx)				
Day 1: 2 Hour Post-dose				
n	xx	xx	xx	xx
Low	xx	xx (xx.x%)	xx (xx.x%)	xx (xx.x%)
Normal	xx	xx (xx.x%)	xx (xx.x%)	xx (xx.x%)
High	xx	xx (xx.x%)	xx (xx.x%)	xx (xx.x%)
Day 8				
N	xx	xx	xx	xx
Low	xx	xx (xx.x%)	xx (xx.x%)	xx (xx.x%)
Normal	xx	xx (xx.x%)	xx (xx.x%)	xx (xx.x%)
High	xx	xx (xx.x%)	xx (xx.x%)	xx (xx.x%)
Day 15				
n	xx	xx	xx	xx
Low	xx	xx (xx.x%)	xx (xx.x%)	xx (xx.x%)
Normal	xx	xx (xx.x%)	xx (xx.x%)	xx (xx.x%)
High	xx	xx (xx.x%)	xx (xx.x%)	xx (xx.x%)
etc.				

Baseline is defined as the last valid, non-missing assessment prior to study drug administration on Day 1. Percentages are based on the number of subjects with data at the specific visit.

**Programming Note:**

- Include all treatment groups: Part A: LMN-101 3000 mg, Part B: LMN-101 300 mg, Part B: LMN-101 1000 mg, Part B: LMN-101 3000 mg, LMN-101 Overall, Placebo.

Sponsor: Lumen Bioscience, Inc. Database Lock: yyyy-mm-dd  
 Protocol: CAM01

Table 14.3.4.4.3 Summary of Vital Signs Shifts from Follow-up (Low, Normal, High) (Safety Analysis Set)

Parameter: Systolic Blood Pressure (mmHg)

Treatment Visit	Follow-up  n (%)	Result Classification		
		Low	Normal	High
Part A: LMN-101 3000 mg (N=xx)				
Screening				
n	xx	xx	xx	xx
Low	xx (xx.x%)	xx (xx.x%)	xx (xx.x%)	xx (xx.x%)
Normal	xx (xx.x%)	xx (xx.x%)	xx (xx.x%)	xx (xx.x%)
High	xx (xx.x%)	xx (xx.x%)	xx (xx.x%)	xx (xx.x%)
Day 1: Pre-dose				
N	xx	xx	xx	xx
Low	xx (xx.x%)	xx (xx.x%)	xx (xx.x%)	xx (xx.x%)
Normal	xx (xx.x%)	xx (xx.x%)	xx (xx.x%)	xx (xx.x%)
High	xx (xx.x%)	xx (xx.x%)	xx (xx.x%)	xx (xx.x%)
Day 1: 2 Hour post-dose				
n	xx	xx	xx	xx
Low	xx (xx.x%)	xx (xx.x%)	xx (xx.x%)	xx (xx.x%)
Normal	xx (xx.x%)	xx (xx.x%)	xx (xx.x%)	xx (xx.x%)
High	xx (xx.x%)	xx (xx.x%)	xx (xx.x%)	xx (xx.x%)
etc.				

Baseline is defined as the last valid, non-missing assessment prior to study drug administration on Day 1. Percentages are based on the number of subjects with data at the specific visit.

## Programming Note:

- Include all treatment groups: Part A: LMN-101 3000 mg, Part B: LMN-101 300 mg, Part B: LMN-101 1000 mg, Part B: LMN-101 3000 mg, LMN-101 Overall, Placebo.

Sponsor: Lumen Bioscience, Inc.  
Protocol: CAM01

Database Lock: yyyy-mm-dd

Table 14.4.1 Summary of Immunology by Timepoint (Safety Analysis Set)

Parameter: Anti-VHH Antibodies (Units)

Treatment Group Visit	Actual Value						Change from Baseline 					
	n	Mean	SD	Median	Minimum	Maximum	n	Mean	SD	Median	Minimum	Maximum
Part A: LMN-101 3000 mg (N=xx)												
Baseline 	xx	xx.xx	xx.xx	xx.xx	xx.x	xx.x	-	-	-	-	-	-
Day 29	xx	xx.xx	xx.xx	xx.xx	xx.x	xx.x	xx	xx.xx	xx.xx	xx.xx	xx.x	xx.x
Part B: LMN-101 300 mg (N=xx)												
Baseline 	xx	xx.xx	xx.xx	xx.xx	xx.x	xx.x	-	-	-	-	-	-
Day 28	xx	xx.xx	xx.xx	xx.xx	xx.x	xx.x	xx	xx.xx	xx.xx	xx.xx	xx.x	xx.x
Day 56	xx	xx.xx	xx.xx	xx.xx	xx.x	xx.x	xx	xx.xx	xx.xx	xx.xx	xx.x	xx.x
Part B: LMN-101 1000 mg (N=xx)												
Baseline 	xx	xx.xx	xx.xx	xx.xx	xx.x	xx.x	-	-	-	-	-	-
Day 28	xx	xx.xx	xx.xx	xx.xx	xx.x	xx.x	xx	xx.xx	xx.xx	xx.xx	xx.x	xx.x
Day 56	xx	xx.xx	xx.xx	xx.xx	xx.x	xx.x	xx	xx.xx	xx.xx	xx.xx	xx.x	xx.x
Part B: LMN-101 3000 mg (N=xx)												
Baseline 	xx	xx.xx	xx.xx	xx.xx	xx.x	xx.x	-	-	-	-	-	-
Day 28	xx	xx.xx	xx.xx	xx.xx	xx.x	xx.x	xx	xx.xx	xx.xx	xx.xx	xx.x	xx.x
Day 56	xx	xx.xx	xx.xx	xx.xx	xx.x	xx.x	xx	xx.xx	xx.xx	xx.xx	xx.x	xx.x
etc.												

SD: Standard Deviation

Baseline is defined as the last valid, non-missing assessment prior to study drug administration on Day 1.

## Programming Note:

- Include all treatment groups: Part A: LMN-101 3000 mg, Part B: LMN-101 300 mg, Part B: LMN-101 1000 mg, Part B: LMN-101 3000 mg, LMN-101 Overall, Placebo.

Sponsor: Lumen Bioscience, Inc.  
Protocol: CAM01

Database Lock: yyyy-mm-dd

Table 14.4.2 Summary of Immunology Shifts from Baseline (Low, Normal, High) (Safety Analysis Set)

Parameter: Anti-VHH Antibodies (Units)

Treatment	Visit	Baseline  n(%)	Post-dose Result Classification		
			Low	Normal	High
LMN-101 25 mg (N=xx)					
Day 2					
	N	xx	xx	xx	xx
	Low	xx	xx (xx.x%)	xx (xx.x%)	xx (xx.x%)
	Normal	xx	xx (xx.x%)	xx (xx.x%)	xx (xx.x%)
	High	xx	xx (xx.x%)	xx (xx.x%)	xx (xx.x%)
Day 5					
	N	xx	xx	xx	xx
	Low	xx	xx (xx.x%)	xx (xx.x%)	xx (xx.x%)
	Normal	xx	xx (xx.x%)	xx (xx.x%)	xx (xx.x%)
	High	xx	xx (xx.x%)	xx (xx.x%)	xx (xx.x%)
Day 8					
	n	xx	xx	xx	xx
	Low	xx	xx (xx.x%)	xx (xx.x%)	xx (xx.x%)
	Normal	xx	xx (xx.x%)	xx (xx.x%)	xx (xx.x%)
	High	xx	xx (xx.x%)	xx (xx.x%)	xx (xx.x%)
etc.					

Baseline is defined as the last valid, non-missing assessment prior to study drug administration on Day 1. Percentages are based on the number of subjects with data at the specific visit.

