### **2.3.2 Secondary Endpoints**

The secondary endpoints for this study are:

- Peak serum VHH concentration following administration of the initial dose and peak serum VHH concentration following a course of treatment (if systemic absorption is observed).
- Area under the serum VHH concentration versus time curve (AUC) following administration of the initial dose and following a course of treatment (if systemic absorption is observed).
- Induction of serum anti-VHH IgG antibodies (if systemic absorption is observed).

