### 3.2 Key Definitions

- **Baseline:** The baseline value is defined as the last available valid (quantifiable continuous or categorical value), non-missing observation for each participant prior to first study drug administration. Repeat and unscheduled assessments will be included in the derivation of the baseline values.
- **Change from Baseline:** The change from baseline value is defined as the difference between the result collected/derived at a post-baseline visit/time point and the baseline value.

The change from baseline value at each post-baseline visit/time point will be calculated for all continuous parameters using the following formula:

$$\text{Change from Baseline Value} = \text{Result at Visit/Time Point} - \text{Baseline Value}$$

The change from baseline value will only be calculated if the specific post-baseline visit/time point result and the baseline value for the parameter are both available and will be treated as missing otherwise.

- **Percent Change from Baseline**

Percent Change from Baseline at each post-baseline visit/time point will be calculated for all continuous parameters using following formula

$$\% \text{ Change from Baseline} = 100 \times \frac{(\text{Post-Dose Visit Value} - \text{Baseline})}{\text{Baseline}}$$

- **Study day:** The study day of an event is defined as the relative day of the event starting with the date of the first study drug administration (reference date) as Day 1 (there will be no Day 0).

Relative days for an event or measurement occurring before the date of first dose will be calculated as follows:

$$\text{Relative Day} = \text{Event Date} - \text{Date of First Dose}$$

The relative day for an event or measurement occurring on or after the reference date to the date of the last dose will be calculated as follows:

$$\text{Relative Day} = \text{Event Date} - \text{Date of First Dose} + 1$$

There is no relative Day 0. Relative day will not be calculated for partial dates in cases where relative day is shown in a data listing.

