#### **13.1 Serum anti-VHH IgG antibodies**

Serum samples will be collected at baseline, Day 28 (Part B only), and end of study for measuring for antidrug antibodies if systemic absorption of LMN-101 is observed. If anti-drug antibodies are observed, additional determinations will be performed for antibodies. If antibodies are observed on confirmatory assays, additional testing will be done to measure antibody titers.

Immunogenicity assessments will be listed for all time points.

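### No planned output defines or counts confirmed antibody-positive or newly positive participants, although antibody induction is a secondary endpoint

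*SAP*

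**What the plan says.** SAP 2.3.2 lists as a secondary endpoint "Induction of serum anti-VHH IgG antibodies (if systemic absorption is observed"). SAP 13.1 describes a sequence of tests. Samples are taken at baseline, Day 28 (Part B) and end of study. Then "If anti-drug antibodies are observed, additional determinations will be performed for antibodies", and finally "If antibodies are observed on confirmatory assays, additional testing will be done to measure antibody titers".

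The only analysis in the text of SAP 13.1 is a listing: "Immunogenicity assessments will be listed for all time points". The table list in SAP 17 adds two summaries. The first, "Table 14.4.1 Summary of Immunology by Timepoint (Safety Analysis Set"), carries the line "Parameter: Anti-VHH Antibodies (Units") and shows n, mean, SD, median, minimum and maximum for the actual value and for change from baseline. The second, Table 14.4.2, is "Summary of Immunology Shifts from Baseline (Low, Normal, High) (Safety Analysis Set"). Listings 16.2.11.1 and 16.2.11.2 show a value, a reference range and a High/Low flag for each participant. They have no column for antibody status or for the confirmatory result.

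Under SAP 3.2, change from baseline "will only be calculated if the specific post-baseline visit/time point result and the baseline value for the parameter are both available"; otherwise it is missing. SAP 3.5 does not impute missing safety data, but it allows a result reported as a range to be set to its boundary, for example below 10 to 10.

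**The concern.** Induction asks how many participants without the antibody before dosing have it afterwards. That is a count of people. A mean change in units does not answer it, and a Low/Normal/High shift answers it only if the class boundary is the assay's positivity threshold, which no document states.

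If testing goes ahead, the summary tables would not directly give the number per dose group who developed antibodies. The rule for calling someone positive would also be left open until after the assay results exist. In a first-in-human trial with four active participants per cohort, a single conversion is worth reporting as such.

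**Working it through.** The documents give no figure for this endpoint, so there is none to reproduce. The planned enrolment does agree with its parts: 2 + 3 × (4 + 2) = 20.

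**Inputs from the SAP.** Four active and two placebo participants per Part B cohort (2.5); change missing unless both values exist (3.2); optional replacement of a below-limit result by its boundary (3.5); titer only after confirmation (13.1).

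**Assumptions, because the documents give no values.** The tabulated value is a titer. A negative result either has no number or is reported as below 10. A converter's titer is 40, 160 or 640.

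**Step 1: one converter in a four-person arm, no replacement.** Table 14.4.1 shows baseline n = 0, Day 28 Actual Value n = 1 and change n = 0. This holds at every assumed titer, so the converter is absent from the change column.

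**Step 2: the same arm, below 10 set to 10.** Mean change = (titer − 10)/4.
- Titer 40: 30/4 = 7.5
- Titer 160: 150/4 = 37.5 (SD 75.0, median 0)
- Titer 640: 630/4 = 157.5

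**Step 3: does the mean reveal the number of converters?** All four are negative at baseline, with 10 substituted.

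| Day 28 values | Changes | Mean change | Newly positive |
|---|---|---|---|
| 10, 10, 10, 160 | 0, 0, 0, 150 | 37.5 | 1/4 (25%) |
| 10, 10, 85, 85 | 0, 0, 75, 75 | 37.5 | 2/4 (50%) |
| 47.5 in all four | 37.5 in all four | 37.5 | 4/4 (100%) |

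The mean is the same in all three rows.

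**Step 4: does the Actual Value n reveal it?** Only in part. Suppose two participants convert, one is positive throughout with an unchanged titer, and one stays negative. Without replacement, Actual Value n rises from 1 to 3, while the change column has n = 1 and mean 0. But the n is a net figure: if one baseline positive turns negative while another participant converts, it stays at 1, the change n is 0, and the conversion does not show.

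**Step 5: Low/Normal/High.** SAP 12.3.1 applies these classes to parameters with a defined normal range. Neither document gives a range or cut point for anti-VHH antibodies.

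**Step 6: what a count would show.** One converter in four reads 1/4 (25.0%; exact 95% interval 0.6% to 80.6%), and none reads 0/4 (upper limit 60.2%). For pooled Part B active, 1/12 is 8.3% (0.2% to 38.5%). The intervals only show how little four or twelve people can establish; the plan is descriptive.

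**The case against.** The strongest reply is that nothing is lost. SAP 13.1 plans listings, and Listing 16.2.11.1 shows every participant's values before and after dosing. Its mock even includes an unflagged baseline followed by a High result at Day 29. With four active participants per cohort and no inference planned, a reader can count conversions by hand. In an arm of four, the full row of summary statistics would also separate the three cases in the table above: the maxima are 150, 75 and 37.5. If the laboratory used the assay cut point as its upper limit, the Normal-to-High cell of Table 14.4.2 would count converters. The assay format is itself inferred: the SAP speaks of antibodies being observed and confirmed, and does not say that the first test yields no number.

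Most of this stands, and it rules out several stronger readings. A reader might infer that a converter is counted nowhere; the listings and the Actual Value n contradict that. A reader might infer that the change column can hold only people positive before dosing; SAP 3.5 allows a replacement that would bring converters in. In the mixed cohort of Step 4, with converter titers of 160, changes of 150, 150, 0 and 0 would give n = 4 and mean 75. A reader might infer from the 25 mg arm and Days 2, 5 and 8 in the Table 14.4.2 shell that the table cannot be filled. Those rows are leftovers: the chemistry shift shell shows the same 25 mg arm, and the General Comments to the mock tables and SAP 13.1 give the right groups and visits.

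What the reply does not supply is a definition. Hand counting, back-calculation from summary statistics and a cut point that may arrive later each need someone to decide afterwards what counts as positive.

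**Conclusion.** The point holds in limited form: no planned table or listing defines or counts confirmed-positive or newly positive participants, so the induction endpoint has no matching summary. If the value in Table 14.4.1 is a titer, change is missing for a participant negative at baseline unless a below-limit value is replaced. With replacement, the mean does not show how many converted: 25%, 50% and 100% induction all give 37.5 under the assumed titers. Table 14.4.2 and both antibody listings rely on a range that the documents do not define.

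The documents do not support saying that conversions would be invisible, since they can be recovered by hand. The consequence is also conditional: antibody testing happens only if systemic absorption is observed, and the protocol does not expect absorption (2.1, 7.19). The conclusion rests on reading the test sequence as positive or negative with a titer for confirmed positives; this is reasonable but is not the SAP's wording. It is worth correcting before any antibody data are seen.

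**What to change.** In SAP 13, define positive as confirmed positive. Replace the change and shift summaries in Tables 14.4.1 and 14.4.2 with:
- n/N (%) confirmed positive at baseline, Day 28 (Part B) and end of study (Day 29 in Part A, Day 56 in Part B);
- n/N (%) newly positive, meaning negative at baseline with any later confirmed positive, with N stated.

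Show both by treatment group, including placebo. Report titers in positives only, as median and range. Report treatment-boosted antibodies only if the assay laboratory supplies a variability threshold.

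In Listings 16.2.11.1 and 16.2.11.2, replace the reference range and High/Low flag with screening, confirmatory and titer results. Remove the 25 mg and Day 2, 5 and 8 rows from the Table 14.4.2 shell. Reconcile the analysis set: SAP 13 assigns immunogenicity to the PK set, which excludes participants who receive only placebo (SAP 4.1.2), while the tables use the Safety set and the Table 14.4.1 programming note includes placebo. Without this the denominators are not fixed.

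The cost is SAP wording and shell revision. SAP 3.1 already provides counts and percentages for categorical variables, and no new samples or assays are needed.
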